8.7.2 Sensitivity Efficacy Analysis

8.7.2.1 Sensitivity Analyses for Absolute Change in Lesion Count

The first sensitivity analysis for absolute change in lesion count will use a repeated measures ANCOVA, with treatment, analysis center, visit (i.e., Weeks 2, 4 and 8), and treatment group by visit interaction as independent factors and a covariate of Baseline lesion count. In this analysis, data from all post-baseline visits will be included with no imputation for missing data.

The second sensitivity analysis will use the model based multiple imputation method to impute missing data for the absolute change in lesion counts at Week 12. The multiple imputation will involve 3 principal tasks:

1. Missing values will be filled in 5 times to generate 5 complete data sets. The imputation model used will be an ANCOVA with factors of treatment group and analysis center, and a covariate of Baseline lesion count (i.e., the imputation model will be the same as the analysis model).

Syntax:

```
proc mi data=datain out=dataout seed=&seed. nimpute=5 <options>;  
  class trtpn sitegr1;  
  var trtpn baseline sitegr1 week12;  
  monotone logistic (sitegr1=trtpn baseline);  
  monotone reg (week12=trtpn baseline sitegr1);  
run;
```

2. Each complete data set will be analyzed with an ANCOVA with factors of treatment group, and analysis center, and a covariate of Baseline lesion count. Appropriate modifications will be made should the analysis be based on a non-parametric method.
3. Results from these analyses will be combined into a single inference.

One random seed will be needed to impute the inflammatory lesion counts. The following random seed has been pre-specified by using a random number generator:

Inflammatory Lesion Count Seed=1827396453

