8.7 Analysis of Efficacy

Inflammatory lesion counts will be summarized at each evaluation from Baseline through Week 12. Absolute and percent change in lesion counts will be summarized at Weeks 2, 4, 8, and 12. IGA scores will be summarized from Baseline through Week 12 using descriptive statistics. The dichotomized IGA scores will be summarized at Weeks 2, 4, 8, and 12 using descriptive statistics.

All efficacy results will be presented in by-subject listings.

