8.7.2.2 Sensitivity Analyses for IGA

The first sensitivity analysis for the dichotomized IGA success will use a repeated measures logistic regression model (generalized estimating equations), with dichotomized IGA success as the dependent variable and treatment, analysis center, visit (i.e., Weeks 2, 4 and 8), and treatment group by visit interaction as independent factors. In this analysis, data from all post-baseline visits will be included with no imputation for missing data.

The second sensitivity analysis will use the model based multiple imputation method to impute missing data for the dichotomized IGA data. The multiple imputation will involve 3 principal tasks:

1. Missing values will be filled in 5 times to generate 5 complete data sets. The imputation model used logistic regression with factors of treatment group and analysis center (i.e., the imputation model will be the same as the analysis model).

Syntax:

```
proc mi data=datain out=dataout seed=&seed. nimpute=5 <options>;  
  class trtpn sitegr1 diiga;  
  var trtpn sitegr1 diiga;  
  monotone logistic (sitegr1=trtpn);  
  monotone logistic (diiga=trtpn sitegr1);  
run;
```

2. Each complete data set will be analyzed with a logistic regression a factors of treatment group and analysis center.
3. Results from these analyses will be combined into a single inference.

One random seed will be needed to impute IGA. The following random seed has been pre-specified by using a random number generator:

IGA Seed= 65762814

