Mean	xx.x	xx.x	xx.x	xx.x
SD	xx.xx	xx.xx	xx.xx	xx.xx
Median	xx.x	xx.x	xx.x	xx.x
Min. to Max.	xx to xx	xx to xx	xx to xx	xx to xx
Achieving Clear or Almost Clear				
Success	xx.x%	xx.x%	xx.x%	xx.x%
Failure	xx.x%	xx.x%	xx.x%	xx.x%

^a Ethnicities of Not Reported and Unknown are not included.

Note: Multiple imputation (MCMC) used to impute missing values. Summary statistics represent average values, obtained from averaging the summary statistics generated from each imputed dataset. Negative absolute change values represent decrease from Baseline.

SOURCE: USERNAME\SPONSOR\PROJECT\JOBNAME (DATE, TIME)

Table 14.2.5.1: Sensitivity Analysis of Primary Endpoints: Absolute Change from Baseline in Inflammatory Lesion Count and Dichotomized IGA Success at Week 12
(Intent-to-Treat Population)
(Page 1 of 2)

	E-BPO 5% Cream (N=xxx)	Vehicle Cream (N=xxx)	Skewness P-Value	Treatment P-Value
Inflammatory Lesion Count – Absolute Change from Baseline				
LSMean ^a	xx.x	xx.x	x.xxx ^b	x.xxx ^a
LSSD ^a	xx.xx	xx.xx		x.xxx ^c
Achieving Clear or Almost Clear				
Success	xx.x%	xx.x%	N/A	x.xxx ^d
Failure	xx.x%	xx.x%		

^a Least squares means, standard deviations and treatment p-value from a repeated measures analysis of covariance with factors of treatment group, analysis center, visit and treatment group by visit interaction, and Baseline lesion count as a covariate. Negative least squares means values represent decrease from Baseline.

^b Skewness test based on methods presented by J.H. Zar (1984).

^c P-value from a ranked repeated measures analysis of covariance with factors of treatment group, analysis center, visit and treatment group by visit interaction, and Baseline lesion count as a covariate.

^d P-value from a repeated measures logistic regression with factors of treatment group, analysis center, visit and treatment group by visit interaction.

SOURCE: USERNAME\SPONSOR\PROJECT\JOBNAME (DATE, TIME)

Table 14.2.5.1: Sensitivity Analysis of Primary Endpoints: Absolute Change from Baseline in Inflammatory Lesion Count and Dichotomized IGA Success at Week 12
(Intent-to-Treat Population)
(Page 2 of 2)

	E-BPO 5% Cream (N=xxx)	Vehicle Cream (N=xxx)	Skewness P-Value	Treatment P-Value
Inflammatory Lesion Count – Absolute Change from Baseline				
LSMean ^a	xx.x	xx.x	x.xxx ^b	x.xxx ^a
LSSD ^a	xx.xx	xx.xx		x.xxx ^c
Achieving Clear or Almost Clear				
Success	xx.x%	xx.x%	N/A	x.xxx ^d
Failure	xx.x%	xx.x%		

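### The repeated-measures sensitivity analyses leave Week 12 out of the visit factor and never say that the reported effect is the Week 12 effect

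*SAP*

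**What the plan says.** The first sensitivity analysis of each co-primary endpoint is a repeated-measures model without imputation.

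- **Lesion count (SAP 8.7.2.1).** Besides treatment and analysis center, the terms are "visit (i.e., Weeks 2, 4 and 8), and treatment group by visit interaction as independent factors and a covariate of Baseline lesion count".
- **IGA success (SAP 8.7.2.2).** The GEE logistic model has the same list: "visit (i.e., Weeks 2, 4 and 8), and treatment group by visit interaction as independent factors".
- **Data used.** The next sentence in each section says that "data from all post-baseline visits will be included with no imputation for missing data". SAP 8.7 shows which visits those are: "Absolute and percent change in lesion counts will be summarized at Weeks 2, 4, 8, and 12".
- **Reporting.** Page 1 of Table 14.2.5.1 carries these results under the title "Sensitivity Analysis of Primary Endpoints: Absolute Change from Baseline in Inflammatory Lesion Count and Dichotomized IGA Success at Week 12". Footnote a describes its contents as "Least squares means, standard deviations and treatment p-value from a repeated measures analysis of covariance" and then lists the model terms. Footnotes c (ranked ANCOVA) and d (logistic model) do the same for their p-values. None names a visit.
- **Origin.** Protocol 19.4.8.1 and 19.4.8.2 contain the same three-visit list. SAP section 10 revisits these models and adds the treatment-by-visit interaction, but leaves the list as it was.

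**The concern.** There are two faults, and correcting one does not correct the other.

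First, the visit list is introduced by an i.e., so it reads as a complete definition. A model whose visit factor has levels 2, 4 and 8 cannot estimate a Week 12 effect, yet Week 12 is the time point of both co-primaries and of the table title.

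Second, even with Week 12 restored, a model containing treatment-by-visit has no single treatment effect. Depending on the test and the coding, the ordinary treatment term is an average over visits or the effect at a reference visit. The Week 12 contrast is a different quantity and has to be requested. Two programmers could follow the SAP faithfully and print different estimates and p-values under the same title.

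What is at stake is the value of these models as a check on the Week 12 result. They are the only ITT sensitivity analyses of the co-primaries that impute nothing. Of the two analyses in SAP 8.7.2, they are also the only ones that use dropouts' observed interim data: the model-based multiple imputation works from "var trtpn baseline sitegr1 week12" for lesion count and "var trtpn sitegr1 diiga" for IGA, with no Week 2, 4 or 8 values.

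**Working it through.** **Passages side by side**

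| Place | Visits or time point |
|---|---|
| SAP 8.7.2.1 and 8.7.2.2, visit factor | 2, 4, 8 |
| SAP 8.7.2.1 and 8.7.2.2, next sentence | all post-baseline |
| SAP 8.7, post-baseline efficacy visits | 2, 4, 8, 12 |
| SAP 7.1.1, co-primary endpoints | 12 |
| Table 14.2.5.1, title | 12 |
| Table 14.2.5.1 page 1, footnotes a, c, d | none named |

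The first row conflicts with the four below it, and the last row does not settle which effect is printed.

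**Size, as an illustration**

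The plan states no figure on this point to reproduce, and neither document gives effects before Week 12. The inputs from SAP section 9 are mean changes of -14.1 and -7.4 (difference 6.7), SDs of 6.70 and 17.24, IGA success of 53.3% and 20.0%, and planned n of 234 and 117.

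Three time courses are assumed for the effect at Weeks 2/4/8/12, as fractions of the Week 12 effect: linear (2/12, 4/12, 8/12, 1), fast onset (0.50, 0.70, 0.90, 1) and constant (1 throughout).

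*Lesion count.* Week 12 SE = √(6.70²/234 + 17.24²/117) = √(0.192 + 2.540) = 1.653, so z = 6.7/1.653 = 4.05, unadjusted. For an average over k visits with mean fraction f, equal variances and between-visit correlation ρ, the estimate is 6.7f and z = 4.05 × f/√((1+(k−1)ρ)/k). ρ is taken as 0.5 and 0.7.

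| Course | f, 3 visits | Estimate | z (ρ 0.5 / 0.7) | f, 4 visits | Estimate | z (ρ 0.5 / 0.7) | Week 8 alone |
|---|---|---|---|---|---|---|---|
| Linear | 0.389 | 2.6 | 1.93 / 1.76 | 0.542 | 3.6 | 2.78 / 2.49 | 4.5 |
| Fast | 0.700 | 4.7 | 3.48 / 3.17 | 0.775 | 5.2 | 3.97 / 3.57 | 6.0 |
| Constant | 1 | 6.7 | 4.96 / 4.53 | 1 | 6.7 | 5.13 / 4.60 | 6.7 |

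*IGA.* Week 12 log OR = ln[(0.533 × 0.800)/(0.467 × 0.200)] = 1.518, so OR = 4.57. Its variance is 1/(234 × 0.533 × 0.467) + 1/(117 × 0.2 × 0.8) = 0.0706, so z = 5.72. Both arms' success rates are scaled by the same fractions. The averaged OR is exp(mean log OR). The covariance between visits s and t is the sum over arms of R/(n√(p_s q_s p_t q_t)), with R = 1 when s = t and 0.3 or 0.5 otherwise.

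| Course | OR, 3 visits | z (R 0.3 / 0.5) | OR, 4 visits | z (R 0.3 / 0.5) | Week 8 OR |
|---|---|---|---|---|---|
| Linear | 3.13 | 3.62 / 3.26 | 3.44 | 4.58 / 4.02 | 3.58 |
| Fast | 3.69 | 5.85 / 5.24 | 3.89 | 6.67 / 5.82 | 4.20 |
| Constant | 4.57 | 7.83 / 7.00 | 4.57 | 8.29 / 7.23 | 4.57 |

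Relative to the Week 12 contrast, the lesion z is multiplied by 0.43 to 1.22 (three visits) or 0.62 to 1.26 (four), and the IGA z by 0.57 to 1.37 or 0.70 to 1.45. Averaging shrinks the estimate unless the effect is constant, but it also reduces the variance, so the test can come out weaker or stronger.

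**The case against.** The strongest reply is that this is a drafting slip nobody would act on. The data sentence, the visit schedule, the table title and the link to the primary endpoints in SAP section 10 all point to Week 12. The primary table (14.2.1.2) also leaves the time point to its title. Nothing confirmatory depends on these models. The primary MCMC imputation already uses Weeks 2, 4 and 8, so dropouts' interim data do inform the main Week 12 result. Model-based imputation in ITT and the per-protocol analysis also examine Week 12. The per-protocol analysis is close to observed data there, because non-attenders are excluded (SAP 8.4.4) and treatment failures are set to Baseline (SAP 8.1.5). Finally, the illustration rests on assumed courses, and the lesion z falls below 1.96 only with linear growth and Week 12 left out.

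Most of this stands. Week 12 was very probably intended, the effect is confined to supportive results, and with all four visits no scenario above loses significance. These points bear on priority.

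They do not remove the fault. The primary table can leave the time point to its title because its model has one time point and one treatment term; the interaction model has several possible contrasts, and a title does not choose among them. Use of interim data in the primary imputation does not replace an analysis that avoids imputation.

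**Conclusion.** The point holds. Both repeated-measures sections omit Week 12 from the visit factor and contradict their own next sentence, and no footnote of Table 14.2.5.1 identifies the reported effect as the Week 12 effect. Following the listed visits, or the ordinary treatment term, puts a result other than the Week 12 effect under a Week 12 title for both co-primary endpoints.

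The consequence is limited to supportive analyses; no testing step uses these models. The numerical size is illustrative: it depends on assumed time courses, equal lesion variances across visits and assumed correlations, and it ignores center and baseline adjustment. No direction of bias is claimed. The text should be corrected before unblinding, so that the contrast is not chosen once results are known.

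**What to change.** 1. In SAP 8.7.2.1 and 8.7.2.2, list the visit factor as Weeks 2, 4, 8 and 12.
2. In both sections, prespecify the Week 12 treatment contrast from the treatment-by-visit term as the reported estimate and p-value, for the repeated-measures ANCOVA (unranked and ranked) and for the GEE model.
3. Say the same in footnotes a, c and d on page 1 of Table 14.2.5.1.
4. Record the correction in SAP section 10.

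The cost is wording in three SAP sections, three footnotes on one table shell, and one LSMEANS or ESTIMATE statement per model. No new data are needed. No protocol amendment is needed either, because the SAP's preface says it supersedes the protocol where they differ and the primary analysis does not change.

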8. STATISTICAL AND ANALYTICAL PLANS

8.1 General Methodology

All statistical processing will be performed using SAS® version 9.3 or later unless otherwise stated. Statistical significance will be based on two-tailed tests of the null hypothesis resulting in p-values of 0.05 or less. These methods are intended to analyze the results of the study.

The primary method of handling missing efficacy data will be based on estimation using the method of Markov Chain Monte Carlo (MCMC) imputation. This method provides robust estimation when the pattern of missingness is arbitrary. Additionally, the estimation will be done for each treatment group separately so that the pattern of missingness for one group does not influence the estimation of missing data for another group. Groups of complete datasets following the estimation will be concatenated to form analysis datasets for the comparative analyses and subsequent imputation result inference with SAS PROC MIANALYZE.

Descriptive statistics will also be derived from the multiply imputed datasets.

Additionally, a model-based multiple imputation process will be used as a sensitivity analysis to the MCMC imputation. Finally, the absolute change in lesion count will be analyzed using a repeated measures analysis of covariance (ANCOVA) for lesion count data and a repeated measures logistic regression model (generalized estimating equations) for the dichotomized IGA.

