9. DETERMINATION OF SAMPLE SIZE

The following power calculations are based on the observed Week 12 results of the Phase 2 study, SGT-EBP01-09. This study was a three-arm trial including E-BPO cream, 1% and 5%, and vehicle in the treatment of rosacea. Estimates from the E-BPO cream, 5% arm were used in the power assessments. The anticipated randomization ratio is 2:1 for E-BPO cream, 5% and vehicle, respectively. The computations were performed with nQuery Advisor Version 7.0 using a two-sided test with a statistical significance value of 0.05.

A sample size of 86 in the E-BPO cream, 5% and 43 in the vehicle group has 95% power to detect a statistically significant difference in the proportion of patients who have at least a 2-grade reduction at Week 12 from Baseline in IGA and are clear or almost clear. The estimated percentages with a 2-grade reduction at Week 12 from Baseline in the IGA and clear or almost clear are 53.3% and 20.0% for the E-BPO cream and vehicle, respectively.

A sample size of 200 in the E-BPO cream, 5% and 100 in the vehicle group has 95% power to detect a statistically significant difference in inflammatory lesions. The estimated absolute change from Baseline in treatment means were -14.1 and -7.4 for E-BPO cream and vehicle, respectively, with a standard deviation (SD) of 6.70 and 17.24, respectively.

The sample sizes above will be increased to give a planned enrollment of 234 in the E-BPO cream, 5% group and 117 in the vehicle group since the Phase 3 trial is expected to enroll patients who are as a group more severe than those of the Phase 2 trial. This is a consequence of some changes in the inclusion criteria.

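### The model-based imputation sensitivity analyses ignore the Week 2, 4 and 8 data and remain missing-at-random, so they cannot test the primary analysis's missing-at-random assumption

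*SAP*

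**What the plan says.** **Primary imputation.** SAP 8.1.5.1 and 8.1.5.2 impute lesion counts and IGA by MCMC, separately in each arm, from baseline and Weeks 2, 4, 8 and 12.

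**Second sensitivity analysis.** SAP 8.1 gives its role: "a model-based multiple imputation process will be used as a sensitivity analysis to the MCMC imputation". For lesion counts, 8.7.2.1 specifies "var trtpn baseline sitegr1 week12" and regresses Week 12 on treatment, baseline and center with the arms pooled. The SAP states that this imputation model equals the analysis model. For IGA, 8.7.2.2 specifies "var trtpn sitegr1 diiga", so baseline IGA is left out as well. Neither contains a shift, a reference-based rule or a tipping point.

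**First sensitivity analysis.** This is a repeated measures ANCOVA for lesions and a GEE logistic model for IGA. Of the GEE the SAP says: "In this analysis, data from all post-baseline visits will be included with no imputation for missing data". The ANCOVA is described the same way.

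**Other relevant rules.** SAP 8.1.3 maps early-termination assessments to visits by study day, and those from Day 8 to Day 70 fall in Weeks 2 to 8. SAP 8.1.5 uses LOCF for the PP population. It sets change from baseline to zero for patients who stop because of a treatment-related AE or documented lack of effect, a rule introduced as part of the PP definition. Protocol 13.2 lists lack of efficacy or worsening among the reasons for withdrawal and does not replace those who leave.

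**The concern.** A sensitivity analysis for missing data should relax the assumption under test. The primary assumes that, given arm, baseline and all observed interim values, missingness is unrelated to the unseen Week 12 value. The second sensitivity analysis asks for the same given only treatment, center and, for lesions, baseline. That is a stricter condition. A patient who is doing badly at Week 8 and then leaves is imputed as a typical member of the same arm and center with the same baseline count. A final count taken at early termination before Day 71 is ignored too.

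At stake is the robustness statement for both co-primary endpoints. If the two imputations agree, a reader may take that as evidence against informative dropout, which it is not. If they disagree, the sensitivity analysis may be the one in error.

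**Working it through.** **1. The plan's own figure.** Inputs from SAP 9: "The estimated absolute change from Baseline in treatment means were -14.1 and -7.4 for E-BPO cream and vehicle, respectively", a difference of 6.7, with SDs 6.70 and 17.24. "A sample size of 200 in the E-BPO cream, 5% and 100 in the vehicle group has 95% power". Allocation: "The anticipated randomization ratio is 2:1 for E-BPO cream, 5% and vehicle, respectively". Test level (SAP 8.1): "Statistical significance will be based on two-tailed tests of the null hypothesis resulting in p-values of 0.05 or less".

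- SE at 200/100 = √(6.70²/200 + 17.24²/100) = √(0.224 + 2.972) = 1.79.
- Power = Φ(6.7/1.79 − 1.96) = Φ(1.79) = 96.3%, or 96.0% with the Satterthwaite t, against 95% stated. The planning figure is reproduced.
- The common SD that gives exactly 95% power at 200/100 is 15.2. It serves below as an equal-variance alternative.

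**2. Lesion simulation.** Planned size 234/117, 5 imputations, 300 trials per cell, unranked ANCOVA. The primary was modeled as by-arm normal imputation on baseline and Weeks 2 to 12. The sensitivity analysis was the 8.7.2.1 regression. Assumed, because the documents do not give them: 10% or 20% dropout per arm after Week 4 or Week 8, visit correlations 0.55 to 0.8, the baseline distribution, 12 centers and the dropout mechanisms.

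Bias of the sensitivity analysis in lesions, at 10% / 20% dropout (positive = towards no effect; Monte Carlo error 0.03 to 0.06):

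| Dropout mechanism | SDs 6.70 and 17.24 | SD 15.2 in both |
|---|---|---|
| Depends on baseline only | −0.37 / −0.66 | −0.05 / +0.08 |
| Poor interim response, same in both arms | +1.28 / +2.32 | −0.01 / +0.07 |
| Poor response in vehicle, random in active | +1.79 / +3.21 | +1.41 / +2.57 |
| Poor responders leave vehicle, good responders leave active | +2.07 / +3.83 | +2.80 / +5.10 |
| Not at random: every dropout back to baseline at Week 12 | −0.66 / −1.26 | −0.65 / −1.22 |

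In the first four rows the primary's bias stays between −0.07 and +0.07. In every cell the sensitivity analysis matches complete-case ANCOVA within 0.03 lesions. In the last row the primary's bias is −0.66 / −1.25 and −0.66 / −1.24. The two analyses agree, and both overstate the benefit.

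**3. Direction.** A second simulation (600 trials per pattern, mean baseline about 32, dropout driven by Week 4 response) varied which arm loses more patients. With 7% active / 22% vehicle dropout, the sensitivity analysis gave −5.43 against a true −6.23, an error of 0.80 (13%) towards no effect. With 22% / 7% it gave −6.94 against −6.13, which exaggerates the effect. With 15% in both it gave −6.14 against −6.12.

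**4. IGA.** With success of 53.3% and 20.0% (SAP 9), dropout driven by an assumed Week 4 latent response and assumed correlations of 0.5 to 0.7, completers' rates approximate what the 8.7.2.2 imputation returns. The true difference of 33.3 points became 36.4–37.7 with 22% / 7% dropout, 31.8–32.2 with 7% / 22%, and 34.3–34.9 with 15% in each arm.

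**5. Where the result would tip at planning values.** A shift of δ in imputed active-arm counts moves the estimate by δ × the missing fraction. SE at 234/117 = √(6.70²/234 + 17.24²/117) = 1.65, without inflation for missing data. Significance is lost when the difference falls to 1.96 × 1.65 = 3.24, a loss of 3.46 lesions. That is δ ≈ 3.46/0.10 = 35 lesions with 10% missing, or 3.46/0.20 = 17 with 20%.

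**The case against.** The strongest reply has four parts.

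- **The plan does depart from missing at random.** SAP 8.1.5 applies zero change to the patients whose dropout is most plausibly informative, and LOCF to other missing PP data. Both feed the PP analysis of the co-primary endpoints. This stands, so a reader who infers that no planned analysis leaves missing at random goes too far. But both rules are written for PP. The remark that the zero-change step follows the MI process for all subjects leaves its reach into ITT unclear.
- **The lesion repeated measures ANCOVA uses the interim visits.** This also stands: the discarding of data concerns the second analysis only. The ANCOVA nevertheless remains missing-at-random.
- **The second analysis does vary real features.** It pools arms, puts center in the imputation model and, for IGA, imputes the dichotomized outcome by logistic regression instead of rounding a normal draw. So it is too strong to say that it tests nothing about the primary result. What it cannot test is the missing-at-random assumption.
- **The consequence may be small.** The bias figures depend on assumed inputs, nearly vanish with symmetric dropout and equal SDs, and often run against the product. Both tipping shifts in step 5 exceed the planned active-arm improvement of 14.1 lesions. This limits the severity, though observed effects and dropout may differ from the planning values.

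A reader might also infer that the GEE is weaker still than the IGA imputation. That is not shown. In a small check (25 trials per pattern, 7% / 22% dropout), the full-data difference was 0.336; complete-case and independence GEE both gave 0.318, and exchangeable GEE gave 0.325.

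**Conclusion.** The point holds in a limited form. The SAP code shows that the model-based imputations drop the interim data and, for IGA, baseline too. They impose a stricter missing-at-random condition than the primary and act like a complete-case analysis. They cannot show whether the primary survives informative dropout.

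Their own bias is conditional. It is about 0 with symmetric dropout and equal SDs, and roughly 1 to 3 lesions or more (5.1 in the most extreme case) when dropout follows interim response differently by arm or the SDs differ. The direction depends on who leaves. These sizes rest on assumed dropout rates, mechanisms and correlations; the structural conclusion does not.

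Nothing here shows that the primary estimate is wrong. It was nearly unbiased whenever dropout depended only on observed data. The gap is that no analysis outside missing at random is clearly specified for ITT. It should be closed, but it does not threaten the design.

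**What to change.** Before unblinding, replace or supplement the second sensitivity analysis for both co-primary endpoints with a prespecified ITT tipping-point analysis.

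- Build it on the primary by-arm imputation with baseline and Weeks 2 to 12. Use MCMC or FCS for intermittent gaps. Adding the interim visits to the MONOTONE statements alone is not enough: it requires a monotone pattern, whereas SAP 8.4.4 tolerates a missed visit before Week 12. It would also nearly repeat the primary.
- Worsen imputed active-arm Week 12 values in fixed steps: lesions added back for the count (for example 0, 2, 4 and so on), lower odds of success for IGA. Report the shift at which each co-primary loses significance.
- State in SAP 8.1.5 whether the zero-change rule applied after the MI process covers ITT or only PP.

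The cost is a little programming and one table, with no new data. The imputation model would no longer equal the analysis model as Protocol 19.4.8 describes, which SAP 10 should record. The robustness statement may become less favorable.
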